## **Study Objectives**

The objective of this project is to define the effectiveness and therefore the role of NIR vein finders in adult patients with difficult peripheral venous access. The specific objective of the proposed randomized controlled trial is to test the clinical success rate of placing peripheral venous catheters in 'difficult' access patients using traditional peripheral venous catheter placement compared to two established methods utilizing NIR vein imaging. We hypothesize that the capability to successfully place lasting peripheral venous catheters is increased with the adjunct of the imaging technology, reducing the number of failed needle sticks, reducing the number of peripheral venous catheters placed throughout a patient's hospital stay, and reducing the need for more invasive catheters such as PICC lines. To test this hypothesis, we utilize a commercially available FDA-approved NIR vein finder which currently is already in clinical use at Lahey Hospital & Medical Center. We are planning to conduct a randomized controlled trial recruiting patients who as part of their routine clinical care will require placement of a peripheral venous catheter and who are considered to have a difficult peripheral venous access. Potential study patients will be randomized into 3 groups:

- Placement of peripheral venous catheter using conventional methods
- Use of a VeinViewer to visualize the most suitable target. Once the target has been identified and marked, the device will be placed aside and the peripheral venous catheter will be placed using conventional methods
- Identification of the most suitable target and placement of a peripheral venous catheter under constant imaging with a VeinViewer

To achieve the goals of this project, we have assembled a highly interdisciplinary team with expertise in clinical peripheral venous catheter placement, biomedical device development, and biostatistics to pursue the following specific aims:

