### Peripheral Venous Cannulation and Randomization of Study Groups

Patients, who meet eligibility criteria and agree to participate in the study after an informed consent process, will undergo simple randomization. A sealed envelope holding the information of the random assignment will be opened by the Vascular Access Team member. Randomization will assign study patients into 1 of 3 groups/treatment arms with a 1:1:1 ratio:

- Placement of a peripheral venous catheter using conventional methods
- Use of VeinViewer to visualize the most suitable target. Once the target has been identified and marked, the device will be placed aside and the peripheral venous catheter will be placed using conventional methods
- Identification of the most suitable target and placement of a peripheral venous catheter under constant imaging with VeinViewer

When the VeinViewer device will be utilized, multiple areas on the patient's upper extremities will be assessed looking for the most suitable access point according to routine clinical practice. There is no restriction in regards to vein diameter, vein length, or relation of veins to joints. The choice of the location for intravenous cannulation, the use of tourniquets, the use of heating devices, and any techniques to palpate the vein will be left to the discretion of the Vascular Access Team member based on routine clinical practice. This study requires an unobstructed view of the subject's arm under standard hospital lighting conditions.

Investigators have up to 30 minutes or ONE attempt before the study allows for change of technique to the preference of the Vascular Access Team member.

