### **Data Collection**

*The following variables will be assessed for all study patients at the time of peripheral venous cannulation:*

a) primary outcome measures:

- rate of successful initial placement of a peripheral venous catheter (investigators have up to 30 minutes or ONE attempt before the study allows for change of technique to the preference of the Vascular Access Team member)

b) secondary outcome measures:

- number of required needle sticks before successful placement of a peripheral venous catheter
- type of method that resulted in successful placement of a peripheral venous catheter
- number of visible veins suitable for cannulation (each continuous vein will be counted as one cannulation site)
- IV catheter gauge size utilized after completion of IV cannulation
- target vein location (bend of the elbow, forearm, back of hand, other) and side of extremity (right vs. left)
- use of warming of arm
- procedure time
- procedure associated complications
- Vascular Access Team member experience (years in practice)
- Vascular Access Team member survey:
  - subjective difficulty locating a suitable vein
  - subjective difficulty of venous access
  - subjective reasons for the difficulty of identifying veins
  - subjective impression of locating additional veins with VeinViewer device
  - subjective impression of usefulness of the VeinViewer device in successful placement of a peripheral venous catheter
- Patient survey:
  - usual number of IV attempts required
  - patients' satisfaction after completion of IV cannulation

c) clinical patient demographics will be derived from patient history and/or medical records:

- age
- gender
- height

- weight
- dominant hand
- date of procedure

*The following variables will be assessed for all in-patient study subjects, if available, at the time of follow-up:*

- catheter patency / need for replacement of catheter / type of catheter used for replacement
- presence of complications such as :
  - hematoma
  - phlebitis
  - thrombophlebitis
  - infiltration
  - nerve damage

All abstracted data, including a study number for each patient, will be stored on a password-protected research database on a hospital server at Lahey Hospital & Medical Center. Any identifier, except for date of procedure, will be removed after the follow-up has been completed.

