### **Data Analysis and Statistical Methods**

Direct study group comparison of the primary and secondary outcome variables will be performed using routine statistical tests utilizing a statistician at Tufts CTSI. In addition, the study will collect limited descriptive information pertinent to the effectiveness of visualizing superficial peripheral veins.

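### The needle-stick outcome has no value for a patient who is never cannulated, and the plan gives no rule for such patients; the gap is confined to secondary outcomes.

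*Combined protocol and SAP*

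**What the plan says.** The Data Collection section, under secondary outcome measures, lists the "number of required needle sticks before successful placement of a peripheral venous catheter". Two neighbouring items have the same form: the "type of method that resulted in successful placement of a peripheral venous catheter" and the "IV catheter gauge size utilized after completion of IV cannulation". All three stand under a heading that reads "The following variables will be assessed for all study patients at the time of peripheral venous cannulation".

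The section on cannulation and randomisation limits the assigned technique: "Investigators have up to 30 minutes or ONE attempt before the study allows for change of technique to the preference of the Vascular Access Team". It gives no maximum number of sticks and does not say when peripheral attempts end.

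The Data Analysis and Statistical Methods section says only: "Direct study group comparison of the primary and secondary outcome variables will be performed using routine statistical tests". No section states what is recorded or analysed for a patient who leaves the episode without a peripheral catheter.

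In Study Objectives, the hypothesis includes "reducing the number of failed needle sticks".

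**The concern.** A count of sticks up to success exists only where success occurs. The trial enrols patients with difficult access, some of whom have already failed an attempt, and its hypothesis looks for less use of PICC lines. Some patients may therefore never be cannulated peripherally. Whether a patient is cannulated is decided after randomisation and may depend on the arm.

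If the analyst uses the outcome as worded, patients without a catheter supply no value, and the comparison is no longer between the randomised groups. If the device improves success, the control arm loses more of its worst cases, so a true benefit is understated. Otherwise the analyst has to invent a rule after the data are in. At stake is the evidence for one stated part of the hypothesis.

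**Working it through.** **The plan's own figure.** The documents give no figure for needle sticks. The only related figure is the primary sample size: 50% versus 70%, two-sided 0.0167, 80% power, 125 per group. The pooled two-proportion formula gives n = [2.393 × √(2 × 0.6 × 0.4) + 0.842 × √(0.25 + 0.21)]² / 0.20² ≈ 124.2, so 125. It reproduces, and this point does not touch it.

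**Inputs.** First-stick success p is 50% (control) and 70% (device), taken from the sample-size section. Treating those rates as first-stick rates is an assumption. So are the later-stick success r (30-50%) and the stopping point K (2, 3 or 6 sticks), because the documents give neither.

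**Formulas.**
- P(1) = p, and P(k) = (1 − p)(1 − r)^(k−2) r for k = 2 to K
- Never cannulated: F = (1 − p)(1 − r)^(K−1)
- S = Σ k P(k)
- Mean among successes: S / (1 − F)
- Mean in all patients, failures scored at sticks made: S + K F
- Mean in all patients, failures scored one above the last stick: S + (K + 1) F

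**Worked case, K = 3, r = 40%.**
- Control: P = 0.50, 0.20, 0.12; F = 0.18; S = 1.26. Means: 1.26 / 0.82 = 1.537; 1.26 + 0.54 = 1.80; 1.26 + 0.72 = 1.98.
- Device: P = 0.70, 0.12, 0.072; F = 0.108; S = 1.156. Means: 1.156 / 0.892 = 1.296; 1.156 + 0.324 = 1.48; 1.156 + 0.432 = 1.588.
- Differences: 0.241 among successes, 0.320 at sticks made, 0.392 with one above.
- Shortfall: 1 − 0.241 / 0.320 = 25%; 1 − 0.241 / 0.392 = 39%.

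**Grid** (shortfall of the success-only difference against each all-randomised difference):

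| K | r | Never cannulated, control / device | Success-only difference | Sticks made: difference (shortfall) | One above: difference (shortfall) |
|---|---|---|---|---|---|
| 2 | 30% | 35.0% / 21.0% | 0.117 | 0.200 (42%) | 0.340 (66%) |
| 2 | 40% | 30.0% / 18.0% | 0.139 | 0.200 (30%) | 0.320 (56%) |
| 2 | 50% | 25.0% / 15.0% | 0.157 | 0.200 (22%) | 0.300 (48%) |
| 3 | 30% | 24.5% / 14.7% | 0.224 | 0.340 (34%) | 0.438 (49%) |
| 3 | 40% | 18.0% / 10.8% | 0.241 | 0.320 (25%) | 0.392 (39%) |
| 3 | 50% | 12.5% / 7.5% | 0.247 | 0.300 (18%) | 0.350 (29%) |
| 6 | 30% | 8.4% / 5.0% | 0.444 | 0.555 (20%) | 0.588 (24%) |
| 6 | 40% | 3.9% / 2.3% | 0.408 | 0.461 (11%) | 0.477 (14%) |
| 6 | 50% | 1.6% / 0.9% | 0.365 | 0.388 (6%) | 0.394 (7%) |

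**Unequal stopping (hypothetical).** Take p = 50% and r = 40% in both arms, so skill is identical. One arm stops after 2 sticks and the other after 4. Never cannulated: 30% versus 10.8%.
- Among successes: 0.90 / 0.70 = 1.29 versus 1.548 / 0.892 = 1.74
- Sticks made: 0.90 + 0.60 = 1.50 versus 1.548 + 0.432 = 1.98
- One above: 0.90 + 0.90 = 1.80 versus 1.548 + 0.54 = 2.09

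All three means favour the arm that fails more. As an ordered outcome (1; 2; 3 or more; never), the arms are 50 / 20 / 0 / 30% versus 50 / 20 / 19.2 / 10.8%, and the early-stopping arm ranks worse. Recording every stick is therefore not enough. Non-cannulation needs its own, worst rank.

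**The case against.** The strongest reply is that the text excludes nobody. The heading says the variables are assessed for all study patients, and recording every stick in everyone is compatible with it. This stands in part. A reader might infer that patients without a catheter are dropped and that only successes are counted, but the documents do not say so. What they leave is an undefined value with no rule, and the heading does not supply one.

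A reader might also infer that 50% of control and 30% of device patients have later results produced by another technique. The documents do not support that. Those are assumed first-placement failures; the plan permits a change of technique and does not require one, and it records which method succeeded. Comparing whole-episode results by assigned arm is a legitimate pragmatic comparison.

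The size rests on assumptions. Technique is free after one attempt in every arm, so operators may persist, and with 6 sticks the never-cannulated share in control falls to about 2-8%. The choice of score for failures also changes the percentages. Both points stand, which is why both scorings and the longer stopping point are shown.

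A gauge cannot exist without a catheter, so for gauge the gap is only one of reporting.

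Finally, ranking non-cannulation worst is a value judgement: stopping after two sticks ranks below success after six. That is true, and the plan should state it as a convention.

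**Conclusion.** The point holds for a secondary outcome. The needle-stick count is undefined for a patient never cannulated, no section gives a rule, and used as worded it compares arms within a group selected after randomisation. The primary endpoint and the sample size are not affected.

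With the same stopping point in both arms, the distortion is towards no difference. Under the stated assumptions it ranges from 6% (stopping after 6 sticks, 50% later success, sticks made) to 66% (stopping after 2 sticks, 30% later success, one above). The never-cannulated share drives it, and the documents do not give that share.

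A reader might go further and infer that the ranking of the arms will be reversed. That needs one arm to abandon peripheral access sooner. It is possible, because operators open the envelope and know the arm, and the Limitations section concedes that they may favour a method. Nothing in the documents shows that it happens.

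**What to change.** In Data Collection, redefine the outcome as the total number of skin punctures in the cannulation episode, by any technique and including the successful one, for every randomised patient.

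In Data Analysis and Statistical Methods, state that it is compared by assigned arm as an ordered outcome (1; 2; 3 or more; never cannulated peripherally, ranked worst) with a rank or proportional-odds test. State that the ranking is a convention. Report for each arm the number never cannulated and the cumulative success by stick, with all randomised patients in the denominator, so that a reader who disagrees with the ranking can see what drives the result. Report gauge descriptively with a category for not placed.

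The cost is a reworded outcome, a few lines of analysis text and a standard test. The small downside is that the result is no longer a simple mean. Nothing in clinical care changes, and no limit on attempts is implied. The change should be made before the data are analysed.

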In the clinical setting, NIR technology has shown to significantly increase the number of identifiable possible cannulation sites compared with normal eyesight [3,4]. However, the improvement in visualization did not automatically translate into improvement in successful cannulation of veins. Specifically, the efficacy of these vein finding devices has shown limited benefit when tested in the pediatric in-hospital population with a nonselective use in all patients. A meta-analysis of 11 RCTs concluded that using NIR light devices did not have an impact on overall failure rate at the first attempt at peripheral intravenous cannulation (PIVC) in pediatric patients [5]. Similarly, in studies evaluating the number of attempts required for successful PIVC found no difference between the NIR light device and traditional methods [6]. Many investigators subjectively felt the NIR device to be helpful; particularly in selected patients [5]. Yet, subgroup analysis did not define the cohort of pediatric patients that would benefit most from this technology. One publication interpreted these outcomes as such that despite improved visualization of superficial veins, successful venous puncture remains heavily dependent on the skills of the operator [7].

The efficacy of NIR vein finders beyond the first line approach, particularly in patients that have failed conventional peripheral venous access methods or in patients that are expected to be a “difficult stick”, is not established. Conflicting results have been reported in the pediatric literature regarding the subjective benefit of NIR light devices in patients with perceived difficult peripheral intravenous access [6]. In addition, knowledge about the efficacy of these devices in the adult inpatient setting is mostly unknown. The aim of the present study is to address these knowledge gaps.

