## **Limitations**

Overall it is felt that the study has a very robust design. Yet, limitations include bias by any Vascular Access Team member who may favor one method and therefore might create more favorable results with the method of subjective preference (observer-expectancy effect and experimenter bias).

The follow-up was felt to be adequate since most complications are expected to present during the hospital stay. However, long-term complications, such as thrombophlebitis, might be slightly underestimated due to its sometimes later presentation even after removal of the catheter or in patients who have been transferred to a different facility with the catheter still in place. Nevertheless, there is currently no reason to believe that long-term outcomes of a successful peripheral venous catheter are dependent on the method of catheter placement and therefore it is not expected that the study results will significantly be affected.

NIR vein imaging might require a learning curve. To minimize the issue, all Vascular Access Team members have been trained with the device and had to use the device independently during routine patient care for at least 20 cases before being able to participate in the study.

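### No operator code is collected, so the primary comparison cannot be stratified by operator or checked for dependence on particular operators

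*Combined protocol and SAP*

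**What the plan says.** - **Data Collection** itemises the variables. The only operator characteristic is "Vascular Access Team member experience (years in practice". A survey asks the team member for impressions of difficulty and device usefulness at the time of the procedure. No operator code is listed there or elsewhere.
- **Limitations** lists "bias by any Vascular Access Team member who may favor one method and therefore might create more favorable results with the method of subjective preference". The only mitigation described is device training and at least 20 earlier uses, which is aimed at the learning curve.
- **Near-infrared Superficial Vein Imaging** reports one publication's view, drawn from pediatric studies, that "successful venous puncture remains heavily dependent on the skills of the operator".
- **Peripheral Venous Cannulation and Randomization of Study Groups** says that patients "will undergo simple randomization" in a 1:1:1 ratio, with no stratification by operator. The team member opens the envelope and chooses site, tourniquet, warming and palpation.
- **Data Analysis and Statistical Methods** is brief: "Direct study group comparison of the primary and secondary outcome variables will be performed using routine statistical tests". No operator term is mentioned.
- **Sample Size and Power Determination** plans 125 per group for 50% versus 70% success at two-sided 0.0167, and enrols 400. Patients are treated as independent.

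**The concern.** A preference that improves one operator's results with one method is an operator-by-arm effect. The operators are not described as masked, and the technique leaves them much discretion, so the mechanism is plausible in this design. To look for it, the analyst must know who made each attempt. Years in practice does not supply this: two operators with equal experience can favour opposite methods. Nor does the survey, which is completed around the procedure, can be coloured by arm and result, and does not ask for a preference held beforehand.

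The gap may be hard to close later. Data Collection and Risks say that patient identifiers other than procedure date are discarded after follow-up. Even if the chart shows who made the attempt, the research database would then have no link back to it. At stake are a check on a bias that the plan names and some precision in the primary comparison.

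**Working it through.** **1. Inputs.** From the protocol: 400 patients, 1:1:1, so about 133 per arm; 50% versus 70%; two-sided 0.0167 (critical value 2.394). Not in the protocol, therefore assumed: K operators, and τ, the between-operator SD of the device effect.

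**2. The plan's own figure.** With pooled variance and no continuity correction, n = [2.394·√(2·0.6·0.4) + 0.842·√(0.25 + 0.21)]² / 0.20² = (1.659 + 0.571)² / 0.04 ≈ 124.3, hence 125. The stated size reproduces. Power is 0.803 at 125 and 0.830 at 133 per arm. There is no operator component.

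**3. Skill differences only.** Patients are randomised individually and operators are not assigned to arms, so skill is balanced in expectation. Simulations of 400 patients (operator-skill SD of 0.5 to 1.0 on the logit scale, same device effect for all) gave a ratio of true to simple standard error of 0.98 to 1.01. Type I error was about 0.014 to 0.019 against 0.0167. The simple test is valid. With the overall rates held at 50% and 70% and a skill SD of 1.0, its power is about 0.83 to 0.84; stratifying by operator raises this to about 0.89. If operators do not differ, stratifying loses about 0.01 to 0.02.

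**4. Device effect varies by operator, average effect zero.** For a conclusion beyond these operators, Var(difference) = 2·0.25/133 + τ²/K = 0.00376 + τ²/K. The standard-error ratio is r = √[1 + (τ²/K)/0.00376], and the true error is 2·[1 − Φ(2.394/r)].

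Example: τ = 0.10, K = 4 gives τ²/K = 0.0025, r = √1.665 = 1.29, and true error 2·[1 − Φ(1.856)] ≈ 0.064.

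| τ (points) | K = 4 | K = 6 | K = 12 |
|---|---|---|---|
| 5 | 0.027 | 0.023 | 0.020 |
| 10 | 0.064 | 0.046 | 0.030 |
| 15 | 0.13 | 0.09 | 0.05 |

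A separate logit-scale simulation with 5, 10 and 20 operators agrees in pattern: 0.057, 0.031 and 0.024 for an operator-by-arm SD of 0.3, and 0.119, 0.063 and 0.040 for 0.5.

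**5. How far a few operators could move the result.** If two of six equally busy operators lift their own device-arm success by 25 points, the arm moves by 2/6 × 25 = 8.3 points. The standard error is √0.00376 = 0.0613, so significance needs 2.394 × 0.0613 = 14.7 points. An 8.3-point shift gives z = 0.083/0.0613 = 1.36 and a significant result about 15% of the time. The ceiling, with both operators going from 50% to 100%, is 2/6 × 50 = 16.7 points.

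**The case against.** Several objections stand, and they limit the point.

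- A reader might infer that unmodelled operator differences make the planned test too liberal. Individual randomisation rules this out for skill differences (step 3). The cited remark on operator skill therefore supports collecting the code for precision, not a claim of inflated error.
- A reader might infer that one or two operators could produce the whole difference. Step 5 does not show that: 8.3 points is below the 14.7 needed for significance and well below the 20-point design difference. Only the extreme ceiling passes 14.7.
- A reader might take operator preference to be the plan's main bias. Limitations names it but does not rank it.
- The analysis section leaves the method open and does not say that operator will be ignored; a stratified test is also routine. Likewise, not listed does not prove not recorded, since a form could carry an identifier. But no section says so, and a stratified test needs the variable.
- Study Endpoints and Sample Size describe an estimate of promise and an initial data set, not a confirmatory claim about all operators. This weakens the case for making operators the unit of inference.
- Operator-level inference for the primary test would be costly. With SE = √(0.46/133 + 0.10²/K) and a t reference with K − 1 degrees of freedom, power for 50% versus 70% is about 0.19, 0.36 and 0.60 for 4, 6 and 12 operators. That argues for keeping such intervals to a sensitivity analysis.

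None of this answers the central gap: without a code, neither stratification nor a by-operator check can be done.

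**Conclusion.** The point holds in a limited form. Under the plan as written, the primary comparison cannot be adjusted for operator, and dependence on particular operators cannot be checked, although the protocol names the mechanism. If operators differ only in skill, the loss is one of precision: about 0.05 to 0.06 of power (0.83 to 0.84 against about 0.89) at an assumed skill SD of 1.0 logit, and less for smaller differences. If the device effect varies by operator, the nominal 0.0167 becomes about 0.02 to 0.13 for conclusions beyond the participating operators. That range assumes 4 to 12 operators and an effect SD of 5 to 15 points. The documents give neither, so they cannot show which end applies. This is a recommended improvement; it does not make the planned comparison invalid for the operators taking part.

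**What to change.** **Data Collection.** Add an anonymous code for the operator who will make the first attempt, written on the form before the envelope is opened. Record each operator's preferred method once, anonymously, before the study starts.

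**Data Analysis and Statistical Methods.** Stratify the primary comparison by operator, for example with Cochran-Mantel-Haenszel, pooling operators with few patients under a rule set in advance. Report operator-by-arm results and results with each operator left out in turn as sensitivity analyses. Use operator-clustered or random-effects intervals at most as a sensitivity analysis.

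**Cost.** One code per form, one question per operator and a few sentences of analysis text. Power falls by about 0.01 to 0.02 if operators do not differ. The operator-by-arm check will have low power, so a null result there should not be read as reassurance. The code will not reveal a preference shared by all operators; the pre-study preference item would at least disclose one.
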